### 5.3 LIFESTYLE CONSIDERATIONS

During this study, participants are asked to:

- Refrain from ingesting greater than two standard drinks/day of alcohol consumption for study duration.
- Refrain from drinking alcohol two hours before bedtime.
- Abstain from ingesting greater than 400 mg/day of caffeine consumption for study duration.
- Abstain from ingesting caffeine after 3 pm for study duration.
- Abstain from ingesting more than five cups or glasses per day of xanthine-containing beverages (i.e., tea, coffee, energy drinks or cola) for study duration.

### 5.4 STRATEGIES FOR RECRUITMENT AND RETENTION

#### Recruitment Strategies

Participant recruitment and enrollment for Le Rêve 3.0 will be performed entirely by a CRO named 83Bar, Inc., who has extensive experience in managing all aspects of clinical trials. Recruitment materials will include (for details see Supplemental materials):

- Digital advertisements to appear on Facebook / Instagram and Google Search
- Landing pages
  - Landing page with embedded lead generation survey
  - Qualified results landing page
  - Not qualified results landing page
- Lead Generation Survey
- Emails
- Text messages
- Call script
- Privacy Policy
- Social Media Editorial Calendar
- Social Media Comment Moderation

**Design and Procedure:** Prospective candidates will see a digital ad on Facebook, Instagram, or Google search. After a prospective candidate clicks on the ad, they will be directed to a dedicated landing page that includes an embedded survey. The survey is designed to pre-screen prospective candidates. Survey respondents that are “survey qualified” will next receive a phone call from an 83bar Contact Center agent. If the prospective candidate answers the call, the agent will dialogue with the prospective candidate using an IRB-approved script (see supplemental materials). The script is designed to provide additional screening for prospective candidates. Interested participants will be provided with electronic consent forms. Information will then be sent to the study activation team for enrollment. Study candidates will also receive confirmation and reminder via email and text message. 83Bar predicts that upon receiving IRB-approval, the recruitment process will take approximately four weeks.

Target Population:

- Self-identify as meeting the study inclusion/exclusion criteria

Subject Recruitment:

- Potential candidates will be recruited from the general population using IRB-approved Facebook/Instagram and Google search advertisements. Potential candidates will complete an IRB-approved online pre-screening survey.
- Pre-screened potential candidates will be contacted by the 83bar Contact Center. The Contact Center will conduct verbal pre-screening using an IRB-approved script (see supplemental materials). If the candidate is interested in participating in the study, candidates that qualify based on online pre-screening and verbal pre-screening will be invited to participate in the study.

Participant Compensation:

- Participants who successfully complete Le Rêve 3.0 will receive a \$100 gift card immediately upon completion of the study. Participants will also be allowed to keep their Whoop™, a non-invasive wearable fitness and health coach, which will be active for a period of up to two months. After this period, if participants desire to continue using the Whoop strap they will be required to obtain a subscription for its use directly from Whoop™.

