### 3 OBJECTIVES AND ENDPOINTS

OBJECTIVES	ENDPOINTS	JUSTIFICATION FOR ENDPOINTS
Primary		
The primary objective is to determine if Defined CBD influences objective measures of sleep physiology.	The primary endpoint is the percentage of time spent in slow wave (Deep) and REM sleep as quantified by a non-invasive wrist-worn sleep-tracking device called Whoop.	Deep and REM sleep are thought to contribute significantly to restorative sleep. We will use an unbiased approach to collect objective data on these sleep stages to determine if Defined CBD increases deep and REM sleep.
Secondary		
The secondary objective(s) are to determine if Defined CBD influences objective and subjective measures of sleep physiology.	Additional objective secondary outcome measures that will be collected on the Whoop device include: Total sleep time, sleep latency, the number of sleep disturbances, time spent in each sleep stage, and the percentage of time spent in each sleep stage.  A modified version of a clinically validated questionnaire entitled the Participant Global Impression (PGI)  will be used to track subjective measures of sleep physiology. This data will be collected from study participants in the form of a brief five-minute survey that will be completed on their smartphone at the end of each four-week treatment period. This survey measures the perception of the study participants of the effects of treatment.	Although some early clinical studies suggest that CBD might help people with insomnia, no studies have addressed if it influences objective and subjective measures of sleep physiology. Therefore, we will include a number of objective and subjective secondary outcome measures in this study to fill this void in knowledge.

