#### Conclusions and Clinical Significance Of Research Findings

Our clinical data with Defined CBD indicates that it significantly increases the percentage of time people spend in REM and restorative (deep plus REM sleep), and that these effects are most pronounced in people suffering from insomnia. Importantly, we were able to replicate the effects of Defined CBD on these sleep physiology parameters in two independent participant cohorts. Furthermore, participants who took Defined CBD could also perceive a benefit of the treatment on their sleep quality, and not a single AE was reported in either clinical study.

REM and restorative sleep appear to be critically important for good brain health, and their absence in human populations is often associated with chronic ailments and diseases. For example, REM sleep has an essential role in the process of learning and memory in the hippocampus, and disruption of REM sleep can lead to cognitive impairment and other manifestations. During sleep, the brain is able to repair and grow cells, tissue, and nerves that regenerate and boost the hormone and immune system. Along with good nutrition, exercise and stress reduction, restorative sleep is vital for your optimal physical, mental, and emotional health. Insufficient restorative sleep increases the risk of disorders, such as high blood pressure, diabetes, obesity, stroke and depression. It's also associated with cognitive decline and Alzheimer's disease.

Defined CBD is composed of a novel formulation of CBD and terpenes that we have shown significantly increases REM and restorative sleep in people with insomnia, and these people could correctly perceive the benefit of this treatment (even though they were blinded to the treatments). We would now like to replicate these exciting preliminary findings in a larger participant cohort under IRB approval.

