### 5 STUDY POPULATION

#### 5.1 INCLUSION CRITERIA

In order to be eligible to participate in this study, an individual must meet all of the following criteria:

- 1) Has provided a signed and dated informed consent form.
- 2) Presence of chronic insomnia defined as self-reported difficulty initiating (latency to persistent sleep >30 min) and/or maintaining sleep (>30 mins awake during the middle of the night, or waking >30 mins before desired waking time on three or more nights per week) for at least 3 months.
- 3) Insomnia Severity Index score >15.
- 4) Male or female aged 25–70 years.
- 5) Is willing to comply with *all* study procedures throughout the entire study, including:
  - Wearing a sleep-tracking device on their wrist throughout entire clinical study.
  - Ensuring that the sleep-tracking device is connected to their smartphone via Bluetooth on a daily basis so that sleep data can be collected on a daily basis.
  - Ensuring that the sleep-tracking device is charged before going to bed each night, ensuring that sleep data can be collected on a daily basis.
  - Is willing to receive and respond to daily text (SMS) notifications for the duration of the entire clinical study.
  - During the treatment phases of the study, is willing to take the treatment for at least four nights in each week.
- 6) On the nights in which the participant takes the treatment, is willing to abstain from excessive alcohol intake (>two drinks/day).

7) On the nights in which the participant takes the treatment, is willing to refrain from drinking alcohol two hours before bedtime.

8) Female subjects who:

-Are postmenopausal, with amenorrhea for at least one year before the screening interview, OR

-Are surgically sterile, OR

-If of childbearing potential agree to practice effective double barrier methods of contraception (e.g., condom + diaphragm; condom or diaphragm + spermicidal gel or foam), from the time of the signing of informed consent through the last dose of study treatment, or agree to completely abstain from intercourse.

9) Self-reported bedtime between 9 pm and midnight on four-seven nights per week.

10) Owns a smartphone.

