## 5.2 EXCLUSION CRITERIA

An individual who meets any of the following criteria will be excluded from participation in this study:

1) Self-reported body mass index > 32 calculated from patient's height (m) and weight (kg); weight (kg)/square height ( $m^2$ ).

2) Insomnia associated with clinically diagnosed sleep apnea (AHI greater than 15 events/hour), or movement disorders such as restless legs, periodic limb movement (PLM) (greater than 30 events/hour or greater than five events/hour with associated PLM arousals).

3) Are currently participating in a formal behavioral therapy program to facilitate sleep.

4) History of epilepsy or seizures.

5) History of liver disease.

6) Serious head injury or stroke within the past year.

7) Psychiatric disorders including major depression, bipolar, anxiety, or schizophrenia.

8) History of suicide attempt or current suicide ideation.

9) Evidence of any clinically significant, severe or unstable, acute or chronically progressive medical or surgical disorder (including planned medical procedures that may impact sleep), or any condition that may interfere with the absorption, metabolism, distribution, or excretion of the study drug.

10) Patients with a history of cardiovascular disease including poorly controlled hypertension, ischemic heart disease, arrhythmia, or severe heart failure.

- 11) Untreated metabolic disorder such as diabetes.
- 12) Medical conditions that result in frequent need to get out of bed (e.g. nocturia).
- 13) History of drug or alcohol abuse, including past or present history of cannabis dependence.
- 14) Inability to refrain from greater than two standard drinks/day of alcohol consumption for study duration.
- 15) Current cigarette smoker.
- 16) Currently chronic (daily) cannabis user.
- 17) Use of any substance with psychotropic effects or properties known to affect sleep/wake, including neuroleptics, morphine/opioid derivatives, antihistamines, stimulants, anti-depressants, clonidine, within one week prior to screening.
- 18) Use of any over-the-counter sleep medications including tryptophan, valerian root (*Valeriana officinalis*), kava (*Piper methysticum* Forst), melatonin, St John's Wort (*Hypericum perforatum*), Alluna (herbal sleep supplement with valerian root), and hemp within one week prior to screening.

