### 6.3 MEASURES TO MINIMIZE BIAS: RANDOMIZATION AND BLINDING

After enrollment, study participants will be assigned a study participant number, and will be randomized to receive Defined CBD or the Placebo control first. As Le Rêve 3.0 is a crossover study, participants who are randomized to receive Defined CBD as the first treatment will cross-over to receive the Placebo Control as the second treatment, and vice-versa. Both the study participants and the PI will be blinded to the study treatments. Unblinding will occur at the completion of the study by the PI. In certain rare instances (e.g. for a SAE), the blind may be broken for an individual participant by the PI.

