A modified version of a clinically validated questionnaire entitled the PGI will be used to track subjective measures of sleep physiology. This data will be collected from study participants in the form of a brief five-minute survey that will be completed on their smartphone at the end of each four-week treatment period. This survey measures the perception of the study participants of the effects of treatment.

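### The protocol does not hide Whoop sleep scores or coaching from participants, so the PGI may be influenced by the readout and cannot be read as perception independent of the device

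*Combined protocol and SAP*

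**What the plan says.** - **The device is the primary measure.** Section 3 defines the primary endpoint as "the percentage of time spent in slow wave (Deep) and REM sleep as quantified by a non-invasive wrist-worn sleep-tracking device called Whoop".
- **Participants carry it and pair it with their own phone.** Inclusion criterion 5 (section 5.1) requires "Wearing a sleep-tracking device on their wrist throughout entire clinical study" and "Ensuring that the sleep-tracking device is connected to their smartphone via Bluetooth on a daily basis".
- **What kind of device it is.** The compensation paragraph in section 5.4 lets participants keep the Whoop and describes it as "a non-invasive wearable fitness and health coach, which will be active for a period of up to two months".
- **What is blinded.** Section 6.3 states: "Both the study participants and the PI will be blinded to the study treatments". Section 6.1.1 supports this with capsules matched in look, feel and smell. Neither section mentions device output.
- **Participants know when the period changes.** Under section 6.2.2 the packs are labelled Treatment 1 and Treatment 2.
- **The subjective measure.** The PGI is completed on the smartphone at the end of each four-week period. Section 8.1 says: "This survey measures the perception of the study participants of the effects of treatment".
- **How earlier PGI data were read.** The conclusions in section 4.2 say of the earlier studies that "these people could correctly perceive the benefit of this treatment (even though they were blinded to the treatments".

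Sections 6.4 and 10.1.8 describe the study team's daily checks of the device data. The lifestyle rules in section 5.3 say nothing about app use. No readable section hides scores, asks participants not to look, records whether they looked, or collects a treatment guess.

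**The concern.** The trial has an objective measure (deep plus REM percentage from the Whoop) and a subjective one (the PGI). A PGI difference adds evidence beyond the device only if participants answer from how they felt they slept. If they can open an app and compare their scores in Treatment 1 with those in Treatment 2, they may answer from the screen.

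A crossover makes this easier, because each person experiences both periods and knows where one ends and the next begins. Baseline is recorded on the same device. In the earlier studies the PGI was rated against baseline sleep (section 4.2), so a participant could have device scores for both sides of that comparison.

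What is at stake is the interpretation of the secondary subjective objective. The section 4.2 conclusions take PGI results as blinded perception of benefit. If the same inference were drawn from Le Rêve 3.0 while scores were viewable, an apparently confirmatory PGI could simply repeat the device result.

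**Working it through.** **Text check.** Setting sections 3, 5.1, 5.3, 5.4, 6.1.1, 6.2.2, 6.3, 6.4, 8.1 and 10.1.8 side by side gives a participant-worn, phone-linked device that measures the primary endpoint, blinding of allocation only, and no statement on what participants may see.

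**The plan's own figures (section 9.2).** These are 100 participants, at least 90% power, a 15% difference, dropout of at most 33% and 150 enrolled.

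- Enrolment: 100 / (1 − 0.33) = 149.3, rounded up to 150. This reproduces.
- Power: it cannot be reproduced, because no SD is given and the 15% is not stated to be absolute or relative. It can be back-solved. For a paired comparison, two-sided alpha 0.05 and 90% power, δ / SD_d = (1.960 + 1.282) / √100 = 0.324, where SD_d is the SD of a participant's between-period difference. That corresponds to SD_d = 15 / 0.324 = 46.3 points if 15% is absolute, or 6 / 0.324 = 18.5 points if it is relative to an assumed level of 40%. The ratio is 0.324 either way, and only the ratio is used below.

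**Share of participants whose own mean score is higher on active.** This is Φ(δ / SD_d), assuming normal differences, no period effect, and a true effect equal to the planned one.

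| Reading of the power statement | δ / SD_d | Share higher on active |
|---|---|---|
| Paired, 90% power | 0.324 | 63% |
| Paired, 95% power | 0.360 | 64% |
| Paired, 99% power | 0.429 | 67% |
| Two groups of 50, correlation 0 between periods | 0.458 | 68% |
| Two groups of 50, correlation 0.8 | 1.025 | 85% |

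For the last two rows the standardised difference is 3.242 × √(2/50) = 0.648, divided by √(2(1 − ρ)). Because section 9.2 claims at least 90% power, 63% is a floor under the planned effect. With no true device effect the share is 50%.

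**How far the PGI could echo the device.** Suppose the treatment has no direct effect on perceived sleep, but the PGI difference follows the visible score difference with correlation r (an assumption; the documents give none). The standardised PGI effect is then r × 0.324 and its expected z at n = 100 is r × 3.242. The chance of p < 0.05 is Φ(r × 3.242 − 1.96) + Φ(−r × 3.242 − 1.96):

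| r | Expected z | P(PGI p < 0.05) |
|---|---|---|
| 0 | 0 | 5% |
| 0.1 | 0.32 | 6% |
| 0.3 | 0.97 | 16% |
| 0.5 | 1.62 | 37% |
| 0.7 | 2.27 | 62% |

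If the device effect is null, the probability stays at 5% whatever r is.

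**The case against.** **No section says that participants see scores or coaching.** This stands. Section 5.1 requires wearing, connecting and charging, and no more. The description as a coach sits in a compensation paragraph about keeping the device; it shows what the device is, not what it displays during the study. Visibility is therefore an inference, and the supplemental materials and removed pages could not be checked. The gap remains, because the readable plan permits viewing.

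**Blinding is intact.** A reader might infer that visible scores unblind participants. The documents do not support this: capsules are matched and order is randomised, so a score difference hints at allocation only as far as the device effect is real.

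**Most participants could not reliably tell the periods apart.** A reader might take night-to-night noise over 28 nights and conclude that nearly everyone could pick the active period. That needs an SD the documents do not give. It also ignores between-person variation in response, drift and missing nights, and it assumes participants average all 28 nights. The plan's own power statement supports only the 63% floor.

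**The primary endpoint is not shown to be harmed.** A reader might liken coaching to what exclusion criterion 3 (section 5.2) keeps out: "Are currently participating in a formal behavioral therapy program to facilitate sleep". That criterion concerns formal programmes, so the comparison is a stretch. Any coaching would run through baseline and both periods, and randomised order balances time trends in expectation. Added noise is possible; bias is not shown, nor is any change in dosing, alcohol use or dropout.

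**The section 4.2 statements concern earlier studies.** This is true, and the earlier PGI effect is reported there as not statistically significant. For this trial, sections 3 and 8.1 call the PGI a measure of perceived effects and do not claim independent confirmation. Section 4.2 shows only how such a result is likely to be read.

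**Conclusion.** The concern holds as an unaddressed route of influence on a secondary endpoint. If the app shows scores, the PGI may be influenced by them and cannot stand as perception independent of the device. If the screens are already masked, one sentence in section 6.3 settles the matter.

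The size is conditional. Under the planned effect, at least about 63% of participants would have a visible score difference favouring active. At assumed correlations of 0.3 to 0.7, a PGI with no direct treatment effect would reach significance in 16% to 62% of trials. This rests on visible scores, a real device effect of the planned size, a paired reading of section 9.2, and the assumed correlation. It does not support a claim that blinding fails, that the PGI test has inflated type I error under a null device effect, or that the primary analysis is biased. It is worth correcting before enrolment, because viewing cannot be reliably reconstructed afterwards.

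**What to change.** 1. In sections 5.3 and 6.3, state that sleep-stage, sleep-performance and coaching screens are hidden from participants from Day 1 until their last survey, where the device account allows it. The documents do not show whether it does.
2. Where it does not, instruct participants not to open those screens during that time.
3. Release each participant's data to them afterwards.
4. Add two items to each existing end-of-period survey: whether sleep scores were viewed in that period, and a treatment guess. Place both after the PGI questions so that they do not colour the ratings.
5. In section 9.4.3, report the PGI by viewing status descriptively only. Viewers select themselves after randomisation, so agreement among non-viewers should not serve as a decision rule.
6. If scores were viewable, do not present the PGI as independent confirmation of the device result.

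The cost is protocol wording, an account setting or an instruction, two short survey items, and perhaps slightly less participant engagement during the study. N, power and alpha do not change.

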## 6 STUDY INTERVENTION

### 6.1 STUDY INTERVENTION(S) ADMINISTRATION

#### 6.1.1 STUDY INTERVENTION DESCRIPTION

Defined CBD is composed of small capsules made with vegetable cellulose (gluten-free, non-GMO, vegan, certified kosher, certified halal) that contain >99.9% purity hemp-derived CBD dissolved in coconut oil (USDA certified organic, non-GMO, dairy-free, gluten-free, vegan coconut oil) with a custom chemical formulation that also contains highly purified (>98% purity) forms of the terpenes linalool, myrcene, phytol, limonene,  $\alpha$ -terpinene,  $\alpha$ -terpineol,  $\alpha$ -pinene, and  $\beta$ -caryophyllene [Food Grade (GRAS), Natural, Organic, non-GMO, dairy-free, gluten-free, vegan]. Participants will be required to take two small capsules one hour before they go to bed. These capsules will contain a total of 300 mg CBD and 8 mg of terpenes (1 mg of each terpene). Defined CBD contains no  $\Delta$ -9-THC. The capsules that

contain the placebo control will look, feel and smell exactly the same as the capsules that contain Defined CBD, but will contain no CBD or terpenes.

#### 6.1.2 DOSING AND ADMINISTRATION

The dose participants will take in the study is two small capsules, that contain a total of 300 mg CBD and 8 mg of terpenes (1 mg each of the terpenes linalool, myrcene, phytol, limonene,  $\alpha$ -terpinene,  $\alpha$ -terpineol,  $\alpha$ -pinene, and  $\beta$ -caryophyllene) that will be taken orally with a glass of water one hour before bedtime. The participants will be required to take the study medication on a minimum of four nights per week for each of the four-week treatment phases of the study.

